6.3.9. Recording of Adverse Events

Adverse events (AEs) will be recorded by the study doctor during the study in accordance with the Section 8.

6.4. Concomitant therapy

Standard therapy for coronavirus infection (COVID-19, SARS-CoV-2) will be used in accordance with international and national guidelines that will be in force at the time of the study. The patient's status should be monitored during medical care to identify signs of clinical deterioration, such as rapidly progressive respiratory failure and sepsis, and to prescribe relevant treatment. Patients infected with 2019-nCoV should receive supportive symptomatic therapy¹. The comorbid conditions and complications should be treated in accordance with clinical guidelines, standards of medical care for these diseases, conditions, and complications in force in the relevant country at the time of the planned study.

If the concomitant condition is not an inclusion/exclusion criterion, the treatment of such condition within this protocol should follow the standard of care.

¹ Temporary guidelines. Prevention, diagnosis, and treatment of the novel coronavirus infection (2019-nCoV). Version 2 (02/03/2020). Electronic source Access: https://static-1.rosminzdrav.ru/system/attachments/attaches/000/049/329/original/%D0%92%D1%80%D0%B5%D0%BC%D0%B5%D0%BD%D0%BD%D1%8B%D0%B5_%D0%9C%D0%A0_2019-nCov_03.02.2020_%28%D0%B2%D0%B5%D1%80%D1%81%D0%B8%D1%8F_2%29_final.pdf?1580748451, free. Access date: March 16, 2020.

7. ASSESSMENT OF EFFICACY AND PHARMACODYNAMIC EFFECTS

7.1. Efficacy outcomes

According to WHO Master Protocol, the primary endpoint will be evaluated on day 15 of the first part of the study. The day of the primary endpoint may be modified based on a blinded evaluation of various days because there is uncertainty about the clinical course and potential different trajectories according to baseline disease severity¹.

Efficacy outcomes

Primary efficacy outcome

Subject clinical status using the WHO 7-point ordinal scale on day 15 as compared to baseline.

6. Not hospitalized, no limitations on activities.
7. Not hospitalized, limitation on activities.
8. Hospitalized, not requiring supplemental oxygen.
9. Hospitalized, requiring supplemental oxygen.
10. Hospitalized, on non-invasive ventilation or high flow oxygen devices.
11. Hospitalized, on invasive mechanical ventilation or ECMO.
12. Death.

Secondary efficacy outcomes

Clinical severity assessed on scales

1. Subject clinical status using the WHO 7-point ordinal scale

- Time to improvement of each parameter of the primary scale from admission.
- Subject clinical status at days 3, 5, 8, 11, and 29.
- Average change in the clinical status at days 3, 5, 8, 11, 15, and 29 as compared to baseline.

2. The NEWS Score (National Early Warning Score) describes the vital signs (pulse rate, breathing rate, temperature, blood pressure etc.) and its deviation from the reference ranges): is evaluated daily and on day 15.

- The time to discharge or to a NEWS of ≤ 2 and maintained for 24 hours, whichever occurs first.
- Change from baseline to days 3, 5, 8, 11, 15, and 29 in NEWS.

3. Oxygenation, including mechanical ventilation:

- Change (day by day) in the need for oxygenation in the first 28 days (up to day 29).

4. Hospitalization

- Duration of hospitalization (days).

5. Mortality (date, cause)

- 28-day mortality.

6. SOFA scale (evaluation of organ failure associated with sepsis): is evaluated daily and on day 15.

- Change from baseline to days 3, 5, 8, 11, 15, and 29 in SOFA.

7.2. Methods for evaluating, recording, and analysing efficacy outcomes

Efficacy of the study therapy will be evaluated in accordance with the schedule of the study procedures and description of the study parts.

¹ MASTER PROTOCOL. A Multi-centre, Adaptive, Randomized, Double-Blind, Placebo-Controlled Clinical Trial of the Safety and Efficacy of Investigational Therapeutics for the Treatment of COVID-19 in Hospitalized Patients. Electronic source Free access: <https://www.who.int/blueprint/priority-diseases/key-action/multicenter-adaptive-RCT-of-investigational-therapeutics-for-COVID-19.pdf>. Access date: March 13, 2020

8. ASSESSMENT OF SAFETY

8.1. Safety outcomes

The safety will be evaluated throughout the study (from signing the informed consent to the study completion visit) based on the following:

Safety outcomes

Safety parameters

- Cumulative incidence of serious adverse events/reactions (SAEs, SARs)
- Cumulative incidence of adverse events/reaction (AEs, ARs)
- Permanent or temporary discontinuation of infusions/injections (by any cause)
- Clinically significant changes in the levels of leukocytes, haemoglobin, platelets, creatinine, glucose, total bilirubin, ALT, AST, CRP, and other parameters.

The safety of the investigational product will be evaluated based on statistical analysis of the specified parameters.

The investigator is responsible for notifying the Sponsor of any event that seems unusual, including the deviation of the patient's test results from normal values, even if this event can be considered as an unforeseen benefit for the patient.

8.2. Methods and deadlines for assessing, recording, and analysing safety and tolerability outcomes

Surveys related to safety assessment are carried out in accordance with the schedule of the study procedures and a description of the study parts.

8.3. Recording and reporting of adverse events

8.3.1. Definition of Adverse Event (AE)

Adverse event means any untoward medical occurrence associated with the use of an intervention in humans, whether considered intervention related or not. An AE can therefore be any unfavourable and unintended sign (including an abnormal laboratory finding), symptom, or disease temporally associated with the use of medicinal (investigational) product.

Any medical condition that is present at the time that the subject is screened will be considered as baseline and not reported as an AE. However, if the severity of any pre-existing medical condition increases, it should be recorded as an AE.

Given the nature of severity of the underlying illness, subjects will have many symptoms and abnormalities in vitals and laboratory. All Grade 3 and 4 AEs will be captured as AEs in this study.

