ENROLLMENT CRITERIA	
INCLUSION CRITERIA
 
 1. The patient is taking or have been prescribed Polyoxidonium® in accordance with the approved labelling in combination with COVID-19 therapy recommended by the Ministry of Health of the Russian Federation. 2. Verified diagnosis: COVID-19 . 3. Severity of the disease at hospitalization: 
 – severe disease: requiring mechanical ventilation or oxygen, a SpO₂ ≤ 94% on room air or tachypnoea (respiratory rate ≥ 24 breaths/min) – mild-moderate disease: SpO₂ ≥ 94% and respiratory rate ≤ 24 breaths/min without supplemental oxygen. 4. Patients who signed the informed consent. 5. Understands and agrees to comply with planned study procedures. 6. Age ≥18 years old at the enrolment. 7. Has laboratory-confirmed SARS-CoV-2 infection as determined by PCR, or other commercial or public health assay in any specimen prior to enrolment. 
EXCLUSION CRITERIA
 
 1. Pregnancy and lactation. 2. Pathological conditions that make participation in the study impossible for the patient (as judged by the investigator). 3. Participation in any other clinical study during this study, including participation in a clinical study within 30 days before the informed consent. 4. Increased sensitivity to any component of the investigational product. 5. Acute or chronic renal failure. 
WITHDRAWAL CRITERIA
 
 1. The investigator decided that withdrawal from the study is in the patient's interests. 2. Withdrawal of the informed consent (the patient does not want to continue participation in the study). 3. Serious deviation from the study protocol. 4. Idiosyncrasy to the investigational products that developed during the treatment period. 5. AE/SAE that requires an examination and/or treatment that would affect the study procedures significantly. 6. Patient non-compliance. 7. The patient was enrolled by mistake. 8. The patient receives/needs an additional treatment that could affects result of the study or the patient safety. 9. Other conditions or events that require patient withdrawal, as judged by the study doctor.
INVESTIGATIONA	INVESTIGATIONAL PRODUCT

L

**PRODUCT,
DOSAGE,
TREATMENT
REGIMEN**

Polyoxidonium® (azoximer bromide), lyophilizate for solution for injections and topical application.

DOSAGE

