This study is based on medical research goals. Data on treatment received by patients in routine clinical practice will be collected and analysed using epidemiological methods. Patient management, including diagnosis and monitoring of ongoing therapy, will be carried out within the routine clinical practice only. The study does not use unapproved drugs. The drug products will be administered according to the approved instructions for human use and in accordance with generally recognized current routine clinical practice. Compliance with the generally acknowledged current routine medical practice mitigates any additional risks. Thus, participation in this non-interventional study does not expose patients to any additional risks.

Risks related to administration of the investigational product

The following systemic and local adverse reactions are identified in the instructions for human use of Polyoxidonium®: parenteral use: uncommon ($\geq 1/1000$ to $< 1/100$): tenderness, redness, and skin induration in the site of injection; very rare ($\geq 1/10000$): fever, mild anxiety, chills, hypersensitivity to components of the drug (allergic reactions) [IHU].

Additional measures will be taken during screening to ensure safety of the study subjects. The protocol specifies constant medical surveillance over the patients which includes recording and evaluation of adverse events and which will minimise the risks associated with participation in this study.

In case of a known adverse reaction to the drug product, the investigator will take all the

necessary actions, including discontinuation of the drug product. Besides, unknown and unexpected adverse reactions to the investigational product are possible.

This study includes administration of Polyoxidonium®, lyophilizate for solution for injections and topical application, 6 mg (OOO NPO Petrovax Pharm, Russia) in dose of 12 mg once daily intravenously (IV) for 3 days, then every other day intramuscularly (IM) on days 5–17 (the total treatment course is 10 injections).

This dosage regimen is thought to be associated with low probability of adverse events.

Based on the facts described above, the benefit outweighs the potential risks for the patient in the active treatment group.

Risks associated with diagnostic procedures

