4.2. Type/design of the study

This study is an open multi-centre observational study evaluating the efficacy and safety of a non-interventional drug.

The design of a non-invasive non-interventional study was chosen to evaluate the efficacy of the drug in routine clinical practice. Since this study will be non-interventional, all procedures will be carried out in strict accordance with the standards of routine clinical practice and meet the non-interventional criteria set by the Good Pharmacovigilance Practice of the Eurasian Economic Union [approved by the decision of the Council of the Eurasian Economic Commission dated 03.11.2016 No. 87].

No	CRITERION	CONTENT
1	Object, MA	Drug products approved for human use; with a valid marketing authorization
2	Rationale for prescription	As judged by the doctor within the routine clinical practice
3	Time of prescription	Prior to inclusion in the study and regardless of the decision to participate
4	Requirements to the prescription	According to the approved therapeutic indications (therapeutic indications, dosage, etc.)

According to the current routine practice, up-to-date and widely accepted

5	Patient management	clinical guidelines and guides According to the protocol, however, the intervention in the routine management of the patient is minimal
6	Randomization, blinding	Not applicable

The clinical efficacy will be assessed by changes in the patient’s clinical status, duration of hospitalization, oxygenation/mechanical ventilation. The clinical examination will include clinical, laboratory, and instrumental investigations according to the current guidelines on treatment of COVID-19 in the Russian Federation. No additional procedures, except for the special scales (non-invasive), will be carried out during the planned non-interventional study.

The overall objective of the study is to evaluate the clinical efficacy of the investigational product in adult patients hospitalized with COVID-19. The primary endpoint is the patient’s clinical status (in a 7-point ordinal school) on day 15 in accordance with the WHO Master Protocol¹.

The study will be conducted in the clinical centre during hospitalization and outpatient visits of patients to the clinical centre, if necessary.

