5. SCREENING AND WITHDRAWAL OF THE SUBJECTS

5.1. Inclusion criteria

1. The patient is already receiving, or the patient have been prescribed therapy with Polyoxidonium® in accordance with the approved labelling in combination with COVID-19 therapy recommended by the Ministry of Health of the Russian Federation.
2. Verified diagnosis: COVID-19.
3. Severity of the disease at hospitalization:
 - severe disease: requiring mechanical ventilation or oxygen, a $SpO_2 \leq 94\%$ on room air or tachypnoea (respiratory rate ≥ 24 breaths/min).
 - mild-moderate disease: $SpO_2 \geq 94\%$ and respiratory rate ≤ 24 breaths/min without supplemental oxygen.
4. Patients who signed the informed consent.
5. Understands and agrees to comply with planned study procedures.
6. Age ≥ 18 years old at the enrolment.
7. Has laboratory-confirmed SARS-CoV-2 infection as determined by PCR, or other commercial or public health assay in any specimen prior to the enrolment.

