5.2. Exclusion criteria

1. Pregnancy and lactation.
2. Pathological conditions that make participation in the study impossible for the patient (as judged by the investigator).
3. Participation in any other clinical study during this study, including participation in a clinical study within 30 days before the informed consent.
4. Increased sensitivity to any component of the investigational product.
5. Acute or chronic renal failure.

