8.3.5. Time Period and Frequency for Event Assessment and Follow-Up

For this study, all Grade 3 and 4 AEs and all SAEs occurring from the time the informed consent is signed through the study completion (end of study) visit will be documented, recorded, and reported.

Investigators Reporting of AEs

Information on all AEs should be recorded on the appropriate CRF. All clearly related signs, symptoms, and results of diagnostic procedures performed because of an AE should be grouped together and recorded as a single diagnosis. If the AE is a laboratory abnormality that is part of a clinical condition or syndrome, it should be recorded as the syndrome or diagnosis rather than the individual laboratory abnormality. Each AE will also be described in terms of duration (start and stop date), severity, association with the study product, action(s) taken, and outcome.

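### Inclusion criterion 1 conflicts with the Day 1 schedule; if patients already on the drug enrol, stable or resolved reactions to their pre-consent doses are not counted as AEs

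*Combined protocol and SAP*

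**What the plan says.** **Who may enter.** Section 5.1, criterion 1, reads "The patient is already receiving, or the patient have been prescribed therapy with Polyoxidonium". The synopsis has the same rule: "The patient is taking or have been prescribed Polyoxidonium® in accordance with the approved labelling". Neither limits the number of earlier doses or the time since the first one. The design table in section 4.2 gives the time of prescription as "Prior to inclusion in the study and regardless of the decision to participate".

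**When treatment starts.** Section 6.2 makes Day 1 both the enrolment day and the start of treatment, with consent listed in the preliminary evaluation before it. Table 1 puts consent, enrolment and the first of ten doses (days 1 to 17) all on Day 1. It has no entry for doses given before enrolment.

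**What is recorded.** Section 8.1 evaluates safety "from signing the informed consent to the study completion visit". Section 8.3.5 covers Grade 3 and 4 AEs and all SAEs "occurring from the time the informed consent is signed". Section 8.3.1 says "Any medical condition that is present at the time that the subject is screened will be considered as baseline and not reported as an AE"; its next sentence makes any increase in severity of a pre-existing condition an AE.

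**Who is kept out and who is analysed.** Section 5.2, criterion 4, excludes "Increased sensitivity to any component of the investigational product". Section 9.6 defines the safety population by receipt of at least one infusion as prescribed. The safety outcomes in section 8.1 include cumulative incidence of AEs, adverse reactions and SAEs.

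**The concern.** The AE rules fit a study in which nobody has had the drug before consent: consent then precedes all exposure, and whatever is present at screening cannot be due to treatment. Inclusion criterion 1 breaks that premise. For a patient already on the drug, exposure starts before observation does, and a condition present at screening may itself be a drug reaction.

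The reactions listed in section 2.4.2 (injection-site reactions, fever, chills, anxiety, hypersensitivity) could follow any dose, including the earliest. There is a single treated group of at least 50 patients and no control arm against which a loss of early events would show. Section 11.9 requires the report to conclude on the safety profile, and any loss of this kind makes the drug look safer.

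**Working it through.** The plan has no figure to reproduce: the sample size of at least 50 comes without a rate, effect or power. The check is first a reading of the rules against each other, then an illustration on assumed inputs.

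**Step 1: can a patient have a pre-consent dose?** Under inclusion criterion 1, yes, without limit. Under section 6.2 and Table 1, no: consent comes on or before Day 1, and Day 1 carries the first dose. Both cannot hold.

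**Step 2: what happens to a reaction to a pre-consent dose, if there is one?**

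| Course of the reaction | Counted? | Rule |
|---|---|---|
| Resolved before consent | No | 8.1 and 8.3.5, window starts at consent |
| Present and stable at screening | No | 8.3.1, baseline |
| Present at screening, later worsens | Yes | 8.3.1, next sentence |
| Starts after consent | Yes | 8.3.5, whichever dose caused it |

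The two Yes rows remain subject to the grade rule in 8.3.5. Section 6.3.2 collects therapy over the last four weeks, treatments for the current illness and drug allergies. It does not ask for reactions to earlier doses of the study drug.

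**Step 3: selection.** A patient whose earlier dose revealed hypersensitivity is excluded by criterion 4 and so leaves both numerator and denominator. This effect is separate from the loss in Step 2.

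**Step 4: denominator.** Infusions fall on days 1 to 3 only; later doses are intramuscular. A patient enrolled after the third dose could meet section 9.6 only through infusions given before consent, and the section does not say whether those count.

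**Step 5: size, for illustration only.** None of p, f or k is in the documents.

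- p = true risk of at least one AE over the 10-dose course
- f = share of patients already treated at consent
- k = doses of 10 given before consent
- All reactions to pre-consent doses are taken as lost. Any that later worsen are in fact counted, so each result is the upper end for its f and k.

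With constant risk per dose:

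observed = (1 − f)·p + f·[1 − (1 − p)^((10 − k)/10)]

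Example with p = 0.10, f = 0.25, k = 3: 1 − 0.9^0.7 = 0.0711; observed = 0.75 × 0.10 + 0.25 × 0.0711 = 0.0928. The shortfall is 0.0072, or 7.2% of p, and 50 × 0.0072 = 0.36 patients.

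At the other extreme all risk sits on the first dose: observed = (1 − f)·p, so the relative shortfall equals f.

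| p | f | k | Constant risk: observed (relative; patients missed of 50) | First dose only: observed (relative; patients missed of 50) |
|---|---|---|---|---|
| 0.10 | 0.10 | 1 | 0.0990 (−1.0%; 0.05) | 0.0900 (−10%; 0.50) |
| 0.10 | 0.25 | 3 | 0.0928 (−7.2%; 0.36) | 0.0750 (−25%; 1.25) |
| 0.10 | 0.50 | 5 | 0.0757 (−24.3%; 1.22) | 0.0500 (−50%; 2.50) |
| 0.01 | 0.50 | 5 | 0.0075 (−24.9%; 0.125) | 0.0050 (−50%; 0.25) |

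With f = 0, observed = p and there is no bias. The value p = 0.01 is the upper limit of the frequency class that section 2.4.2 gives for injection-site reactions.

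**The case against.** The strongest reply is that the Day 1 schedule governs. Section 4.2 describes the whole 10-injection course as given within the study, and sections 2.5 and 11.6 have the sponsor supplying the drug. On that reading nobody has a pre-consent dose and the bias is zero. This stands as a possible reading, but it leaves inclusion criterion 1 saying the opposite in two places, so an edit is needed either way.

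A reader might infer that reactions to earlier doses are never counted. The documents do not support that: worsening is an AE, and anything that starts after consent falls in the window.

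A reader might also put all the lost reactors in the denominator. Those excluded for hypersensitivity are in neither part of the fraction. Hypersensitivity is also a labelled contraindication in section 2.2, so criterion 4 is not itself a fault in the AE rules.

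The grade rule is a fair further objection. If only Grade 3 and 4 AEs and SAEs are recorded, mild local reactions or chills are lost whatever the consent date. Section 8.3.5 also says that all AEs go on the CRF, so the point is unsettled. Pre-consent Grade 3 and 4 events and SAEs are still lost through timing alone.

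**Conclusion.** The contradiction between inclusion criterion 1 and the Day 1 schedule is certain from the text. The downward bias is conditional: it arises only if already-treated patients enrol, and only through reactions that resolved before consent or stayed stable at screening. Its direction for such patients is clear. Its size cannot be computed, because neither the share pre-treated nor the number of earlier doses is given.

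Two stronger statements are tempting and unsupported. One is that AE incidence is understated, without condition; under the schedule as written it is not. The other is a single figure, for example 30% pre-treated times half of reactions by the third dose, 0.30 × 0.50 = 15% of reactions missed. Both inputs are assumptions with no basis in the documents. In absolute terms the illustration gives at most 2.5 patients of 50 at p = 0.10 and 0.25 of 50 at p = 0.01.

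**What to change.** Reconcile inclusion criterion 1 (section 5.1 and synopsis) with section 6.2 and Table 1, so that it is clear whether a patient may have had doses before consent. If already-treated patients remain eligible:

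- In 8.1, 8.3.1 and 8.3.5, start AE and SAE collection at the earlier of consent or the first dose of the current course. Abstract events since that dose from the hospital chart, and define a baseline condition as one present before that dose.
- Add two eCRF fields: date of first dose and number of doses before enrolment.
- State in 9.6 whether pre-consent infusions count toward the safety population.
- Report AE and SAE incidence overall, and separately for patients observed from the first dose and those already treated.

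The cost is protocol wording, two fields and a short chart abstraction. Pre-consent events would be captured retrospectively, and the incidence may be less favourable. Chart abstraction cannot recover patients who never enrolled because of an early reaction.

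The separate estimates are less precise. With no events the one-sided 95% upper bound is 1 − 0.05^(1/50) = 5.8% for 50 patients and 1 − 0.05^(1/25) = 11.3% for 25. For that reason the split should accompany the overall figure, and patients observed from the first dose should not be made the primary safety set.
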